### **7.3 Subject Population(s) for Analysis**

#### **7.3.1 Safety Lead-In Population**

Subjects are evaluable for DLTs if: 1) they experience a DLT at any time during the DLT evaluation period; or 2) in the absence of DLT have received at least one dose of nivolumab or ipilimumab, have completed RT per protocol, and have completed respective safety assessments without major violations over the entire DLT evaluation period. Patients who are not fully evaluable for DLTs during the DLT evaluation period of 40 days following Day 1 will be replaced.

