### 6.1.1 **Safety Lead-In**

The first 6 subjects enrolled onto the study will be evaluated as a Safety Lead-In cohort. After all screening, registration and baseline procedures are completed as detailed on the Schedule of Events (Appendix 1), subjects will begin the study regimen.

On Day 1 of Cycle 1, subjects will be administered one dose of nivolumab 3 mg/kg IV and one dose of ipilimumab 1 mg/kg IV.

On Day 8 of Cycle 1, subjects will be administered RT to a total dose of 45 Gy, given in 15 fractions of 3 Gy.

CONFIDENTIAL

This material is the property of the NYU School of Medicine. Do not disclose or use except as authorized in writing by the study sponsor

On Day 15 of Cycle 1, nivolumab 3 mg/kg IV will be administered, and subsequently continue once every 2 weeks.

Ipilimumab 1 mg/kg IV will continue once every 6 weeks after the first ipilimumab dose on Cycle 1 Day 1.

The **DLT evaluation period** will be defined as the **first 53 days** on study. The DLT period will start with the first infusion (**Day 1**) and will **end 4 weeks following the final day of radiation**, ie, **Days 1-53**.

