**The first 3 subjects:**

- The first 3 patients in the safety lead-in will be enrolled in a **staggered fashion**, with at least 2 weeks from time of completion of RT to first dose of study drugs for the subsequent patient.
- For the first 3 subjects, the **maximal tumor diameter may not exceed 5 cm**.
- After the 3rd subject is enrolled, **enrollment will halt and subjects will be observed for 40 days for DLTs (see DLT definitions below)** and to assess overall safety. At the end of the DLT period for the first 3 subjects, the safety data will be reviewed by the Sponsor and the NYU DSMC. If 1 or less of the first 3 subjects experiences a DLT during the DLT observation period, the maximal tumor diameter for subsequent subjects may be increased to **6.6 cm**. If  $\geq 2$  of the first 3 subjects experiences a DLT during the DLT observation period, the study will halt and the sponsor, NYU DSMC, and the FDA, may redesign the dosing and schedule of the study treatment or will stop the study for unacceptable toxicity.
- Continuation of enrollment will occur once all of the first 3 subjects have completed the Day 40 safety assessments and the final safety review decisions have been made.

After the first 6 subjects are enrolled, enrollment will stop and subjects will be observed for 40 days for **DLTs**. After all subjects in the Safety Lead-In cohort have completed the DLT observation period, the safety data will be reviewed by the Sponsor and the NYU DSMC. Continuation of enrollment will occur once all of the subjects have completed the Day 40 safety assessments and the final safety review decisions, including whether the study should be discontinued or proceed to phase II, have been made.

If  $\geq 2$  of the first 6 subjects experiences a DLT during the 40 day DLT observation period, the sponsor, and the FDA, may redesign the dosing and schedule of the study treatment or will stop the study for unacceptable toxicity.

If  $\geq 2$  of the first 6 subjects are unable to complete RT due to toxicity related to the planned treatment, the study will be stopped and the overall safety will be re-assessed by the sponsor and DSMC.

If 1 or less of the first 6 subjects experiences a DLT at the end of the 40 day DLT observation period, the study will continue enrollment onto the phase II part of the study.

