DLT will be determined by toxicities related to nivolumab, ipilimumab, or RT during or beginning over the first 40 days of treatment as defined below. Subjects who experience DLT will be discontinued from study therapy and will enter the post-study follow-up phase of the study. Adverse events that meet DLT criteria but occur outside the DLT window will be classified as unacceptable AEs and study treatment will be discontinued.

Subjects are evaluable for DLTs if they have received at least one dose of nivolumab and ipilimumab, have completed RT per protocol, and have completed safety assessments over the entire DLT evaluation period (days 1 through 40). Any subject who discontinues treatment or withdraws from the study prior to completing the DLT evaluation period for any reason other than the occurrence of a protocol-defined DLT or other AE leading to study treatment discontinuation will be replaced. Each replacement patient will be assigned a unique patient number. Any patient who discontinues after the DLT observation period will not be replaced.

CONFIDENTIAL

This material is the property of the NYU School of Medicine. Do not disclose or use except as authorized in writing by the study sponsor

Subjects who do not experience a DLT during the DLT period (40 days) and remain on study after the DLT period will continue nivolumab and ipilimumab administration for up to 2 years or until the subject discontinues study therapy as per protocol. All subjects who discontinue study therapy will enter the post-study follow-up phase of the study.

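### Sections 6.1.1 and 7.3.1 give opposite replacement rules for a lead-in patient who stops for an adverse event that is not a DLT

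*Combined protocol and SAP*

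**What the plan says.** Section 6.1.1 sets the size of the lead-in: "The first 6 subjects enrolled onto the study will be evaluated as a Safety Lead-In cohort". The decision turns on one patient. Enrolment goes on to phase II under this condition: "If 1 or less of the first 6 subjects experiences a DLT at the end of the 40 day DLT observation period". Two or more of six leads to redesign or stopping.

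The two sections then differ on who is evaluable and who is replaced.

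- **Section 6.1.1, evaluability:** "Subjects are evaluable for DLTs if they have received at least one dose of nivolumab and ipilimumab, have completed RT per protocol", together with safety assessments over days 1 to 40. There is no separate clause for a patient who has a DLT.
- **Section 6.1.1, replacement:** a subject who leaves before the end of the period "for any reason other than the occurrence of a protocol-defined DLT or other AE leading to study treatment discontinuation will be replaced". Adverse-event discontinuations are therefore not replaced.
- **Section 7.3.1, evaluability:** patients count if "they experience a DLT at any time during the DLT evaluation period", or if they "in the absence of DLT have received at least one dose of nivolumab or ipilimumab, have completed RT per protocol" and have completed the safety assessments over the whole period.
- **Section 7.3.1, replacement:** "Patients who are not fully evaluable for DLTs during the DLT evaluation period of 40 days following Day 1 will be replaced". Adverse-event discontinuations are not exempt.

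Section 6.1.1 also stops the study if two or more of the first six are "unable to complete RT due to toxicity related to the planned treatment".

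**The concern.** Two operative rules instruct the study team in opposite ways about the same patient, and no other section says which governs. The patient in question stops for an adverse event that is not a DLT and does not finish radiotherapy or the assessments.

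The plan's own rules can produce such a patient. Sections 6.2.4.1 and 6.2.4.2 require both drugs to be stopped for concurrent AST or ALT above 3 x ULN and bilirubin above 1.5 x ULN, while the matching DLT criterion in Section 6.1.1.1 needs bilirubin above 2 x ULN. Between 1.5 and 2 x ULN, discontinuation can be required without an automatic DLT. If the cause cannot be assigned, Section 6.2.7 stops radiotherapy as well. Section 6.9 adds stopping at the investigator's judgement for any adverse event.

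Because 1 of 6 continues and 2 of 6 does not, the handling of one patient can decide the outcome. Who makes up the six should not depend on which section is consulted.

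**Working it through.** The documents give no operating characteristic for the lead-in, so there is no stated figure to reproduce. The check is a comparison of the texts, followed by an illustration with assumed rates.

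**1. The same patient under each section**

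| Patient within the DLT period | Section 6.1.1 | Section 7.3.1 |
|---|---|---|
| Has a DLT | Not replaced | Evaluable, not replaced |
| Stops for a non-DLT adverse event, misses radiotherapy or assessments | Not replaced, not evaluable | Not evaluable, replaced |
| Stops drugs for a non-DLT adverse event, completes radiotherapy and assessments | Not replaced, evaluable | Evaluable, not replaced |
| Leaves for a reason unrelated to toxicity, misses radiotherapy or assessments | Replaced | Replaced |

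Only the second row conflicts.

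**2. One concrete lead-in**

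Take one DLT, four subjects without events, and one dropout of the second-row kind.

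- Section 7.3.1, with a replacement who has no DLT: 1 of 6, continue.
- Section 6.1.1: 1 of 5 evaluable, set against a rule written for six.
- Dropout counted as an event, which neither section provides for: 2 of 6, redesign or stop.

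**3. Five evaluable patients instead of six**

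P(2 or more DLTs) = 1 − (1−r)^n − n·r·(1−r)^(n−1), where r is the DLT rate among evaluable patients (assumed).

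- r = 0.25, n = 6: 1 − 0.178 − 0.356 = 0.466. With n = 5: 1 − 0.237 − 0.396 = 0.367.
- r = 0.30, n = 6: 1 − 0.118 − 0.303 = 0.580. With n = 5: 1 − 0.168 − 0.360 = 0.472.

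This is the consequence of non-replacement under Section 6.1.1. Under Section 7.3.1 the number stays at six.

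**4. Direction of each option**

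Let p be the chance that a patient has a DLT and q the chance of a second-row dropout, both assumed. P(continue) = (1−r)^6 + 6·r·(1−r)^5, with r depending on how the dropout is handled. The separate radiotherapy-completion rule is left out.

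- Not replaced and never counted as an event: r = p.
- Replaced, as in 7.3.1: r = p/(1−q).
- Retained and counted as an event: r = p + q.

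| p | q | Unreplaced, non-event | Replaced | Counted as event |
|---|---|---|---|---|
| 0.10 | 0.10 | 0.886 | 0.863 | 0.655 |
| 0.20 | 0.05 | 0.655 | 0.630 | 0.534 |
| 0.20 | 0.10 | 0.655 | 0.601 | 0.420 |
| 0.20 | 0.20 | 0.655 | 0.534 | 0.233 |
| 0.30 | 0.10 | 0.420 | 0.351 | 0.233 |

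With the threshold fixed at two DLTs, leaving the dropout unevaluable or keeping the dropout as a non-event gives the same DLT count, so the third column covers both readings of 6.1.1.

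**5. How often a single dropout arises**

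The chance of exactly one such dropout in six is 6·q·(1−q)^5: 0.23, 0.35 and 0.39 at q = 0.05, 0.10 and 0.20. The radiotherapy-completion rule needs two, so it cannot act in these cases.

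**The case against.** The strongest reply is that the affected group is small and already watched.

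- A patient with a DLT always stays evaluable under 7.3.1. The DLT definition is broad: related non-hematologic events of grade 3 or above with listed exceptions, and neurological events of grade 2 or above lasting more than 7 days. Most stoppages of radiotherapy for toxicity would already be DLTs.
- Section 6.1.1.1 allows a lower-grade event to be adjudicated as a DLT.
- Two or more failures to complete radiotherapy for related toxicity stop the study separately.
- The Bayesian rule in Section 3.5.1 counts related grade 3 or 4 toxicity and grade 2 toxicity causing discontinuation, with looks at 3 and 6 patients.
- The sponsor and the DSMC review the lead-in data, and Section 7.3.3 keeps every dosed subject in the safety population.

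All of this stands and limits the consequence. None of it removes the conflict: adjudication is discretionary, the radiotherapy rule needs two patients, the Bayesian boundary at six patients is four events, and the safety population governs reporting and not the lead-in decision. It could also be said that the decision rule refers literally to the first six subjects, so that a dropout remains among them. The text does not say so once a replacement has been enrolled.

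A reader might infer that replacement under 7.3.1 makes the lead-in look safer. The documents do not support that as a general statement. It is true only against counting the dropout as an event (0.601 against 0.420 at p = 0.20, q = 0.10), which neither section prescribes. Against leaving the dropout unreplaced as a non-event, replacement is the stricter option (0.601 against 0.655).

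**Conclusion.** The conflict is real and unreconciled, but minor. It concerns only patients who stop for an adverse event not classed as a DLT and who miss radiotherapy or the assessments. Under 7.3.1 one such patient leaves the decision set. Under 6.1.1 the same patient is neither replaced nor evaluable, so the 2-of-6 rule may act on five.

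In that five-patient case the chance of two or more DLTs is 37% instead of 47% at a 25% DLT rate, and 47% instead of 58% at 30%. Those rates, and the p and q used above, are assumptions; the documents supply none. The percentages measure the effect of not replacing and should not be read as the effect of replacement under 7.3.1.

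The documents also do not support the inference that DLTs themselves can be removed by replacement under 7.3.1, or that these patients disappear from safety reporting.

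**What to change.** Use one evaluability and replacement rule, worded identically in Sections 6.1.1 and 7.3.1:

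1. Replace only patients who leave for reasons unrelated to toxicity.
2. State whether an unreplaced adverse-event dropout enters the count of six as an event or a non-event. The choice is the sponsor's, but it must be explicit: aligning the replacement wording alone leaves the count undefined, and keeping such patients as non-events is the most lenient option in the table above.
3. Report all such dropouts to the DSMC at the lead-in review.

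In the same edit, reconcile two related mismatches. Section 6.1.1 requires a dose of nivolumab *and* ipilimumab for evaluability, while Section 7.3.1 requires nivolumab *or* ipilimumab. The DLT window is 53 days in one paragraph of Section 6.1.1; 40 days elsewhere in that section and in Sections 6.1.1.1, 7.3.1 and 8.5; and both 40 and 28 days in the Synopsis and Section 3.1.2. The window determines who has completed the assessments, so the replacement rule cannot be applied until it is settled.

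The cost is a few sentences. No extra patients are needed, since fewer patients would be replaced than under 7.3.1 as it stands.

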#### **7.3.2 Phase II Trial Efficacy Analysis Population**

All subjects that receive at least 1 dose of study drug will be included in the primary analysis for the phase II study, including subjects in the Safety Lead-In treated at the same dose as the phase II subjects.

#### **7.3.3 Safety Analysis Populations**

All subjects who received at least one dose of study drug will be used for the analysis of safety data in this study. Safety summaries will be reported for both the Safety Lead-In and the phase II trial.

At least one laboratory or vital sign measurement obtained subsequent to at least one dose of study treatment is required for inclusion in the analysis of each specific parameter. To assess change from baseline, a baseline measurement is also required.

CONFIDENTIAL

This material is the property of the NYU School of Medicine. Do not disclose or use except as authorized in writing by the study sponsor

### 7.3.4 Surgical Study Cohort Analysis Population

All subjects that receive at least 1 dose of study drug and undergo a craniotomy and tumor re-resection will be included in the safety and efficacy analysis for the Surgical Study Cohort Analysis.

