### *Safety*

Subjects will be evaluated for safety if they have received any study drug. Toxicity assessments will be continuous during the treatment phase. Once subjects reach the survival follow-up phase, either in person or documented telephone calls to assess the subject's status are acceptable. Adverse events and laboratory values will be graded according to the NCI-CTCAE version 4.03.

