### *Endpoints:*

1yr-OS and radiographic response rates will be estimated with exact 95% confidence intervals; with 24 patients, a 95% CI will be no more than 0.4 units wide for the main study cohort. PFS, defined as the time between treatment initiation and first occurrence of disease progression or death, will be censored at last follow-up if the patient remained alive without disease progression. OS will be determined from the time of treatment initiation until the time of death, with OS being censored at last follow-up if the patient remained alive. The Kaplan-Meier curves will be used to summarize PFS and OS and to estimate the medians.

Adverse events will be graded using CTCAE version 4.03. All subjects who initiate therapy (receive at least one dose of ipilimumab and nivolumab and/or radiotherapy) will be evaluated for safety. A Bayesian monitoring approach will be applied to assess safety throughout the Phase II trial with pre-defined stopping rules.

CONFIDENTIAL

This material is the property of the NYU School of Medicine. Do not disclose or use except as authorized in writing by the study sponsor

CONFIDENTIAL

This material is the property of the NYU School of Medicine. Do not disclose or use except as authorized in writing by the study sponsor

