### 6.1.3 Surgical Study Cohort

The Surgical Study Cohort will open, once the Safety Lead-In in the Main Study Cohort is completed. We will use a single-stage design and enroll a total of 16 patients

After all screening, registration and baseline procedures have been completed as detailed on the **Schedule of Events (Appendix 1)**, subjects will begin study treatment as below:

CONFIDENTIAL

This material is the property of the NYU School of Medicine. Do not disclose or use except as authorized in writing by the study sponsor

On C1D-29, all subjects will initiate study treatment with one dose of nivolumab IV (3 mg/kg) followed by one dose of ipilimumab IV (1 mg/kg).

On C1D-15, all subjects in this cohort will undergo craniotomy and tumor re-resection.

On C1D1, all subjects will receive nivolumab IV (3 mg/kg)

On C1D8, all subjects will begin radiotherapy (RT) to a total dose of 45 Gy, given in 15 consecutive fractions of 3 Gy each fraction.

On C1D15, subjects will receive nivolumab 3 mg/kg and ipilimumab 1 mg/kg IV. Thereafter, nivolumab administration will continue once every 2 weeks and ipilimumab administration will continue once every 6 weeks.

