### 7.2 Statistical Methods and Sample Size Determination

#### 7.2.1 Safety

The Safety Lead-In portion of the study will include the first 6 subjects enrolled on the Main Study Cohort. The exact number of patients enrolled in the entire study will depend on the number of protocol-defined DLTs observed and the possibility of opening additional cohorts at modified nivolumab and/or ipilimumab prescriptions as described in Section 6.1.1 (Safety Lead-In). Data for the Safety Lead-In will be summarized using descriptive statistics.

Adverse events will be graded using CTCAE version 4.03. Safety summaries will be reported for both the Safety Lead-In and the phase II trial. All subjects who received at least one dose of study drug and/or radiation will be used for the analysis of safety data in this study. Safety and tolerability will be assessed

CONFIDENTIAL

This material is the property of the NYU School of Medicine. Do not disclose or use except as authorized in writing by the study sponsor

by clinical review of all relevant parameters including adverse experiences (AEs), laboratory tests, and vital signs.

Additionally, specific immune-related adverse experiences (irAEs, as defined Section 6.2.1) will be collected and summarized in separate tables from other AEs by toxicity grade and will include the counts, percentage, and 95% CI.

Adverse events (specific terms as well as system organ class terms) and predefined limits of change in laboratory, and vital sign parameters will be summarized with descriptive statistics (counts, percentage, mean, standard deviation, etc.). Continuous measures such as changes from baseline in laboratory, and vital signs parameters will be summarized using descriptive statistics (mean, standard deviation, etc.) for baseline, on-treatment, and change from baseline values.

For toxicity monitoring statistical methods, see the Primary Safety Endpoints in Section 3.5.

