### 7.2.2 Main Study Cohort - Phase II trial design

A single-stage design will be utilized to estimate overall survival, with a hypothesized 1yr-OS of 60%= $H_1$  and 35%= $H_0$ . We will enroll 24 patients; this design has a two-sided Type I error of 0.05 and a power of 80%.

For endpoint analyses, one year will be defined as 48 weeks (8 cycles) and two years will be defined as 96 weeks (16 cycles). Patients will be evaluated for radiographic responses by conventional contrast enhanced MRI every 8 weeks. Radiographic response assessments will be determined using RANO criteria for GBM.

1yr-OS and radiographic response rates will be estimated with exact 95% confidence intervals; with 24 patients, a 95% CI will be no more than 0.4 units wide. OS will be determined from the time of treatment initiation until the time of death due to any cause, with OS being censored at last follow-up if the patient remained alive. Patients who were last known to be alive and progression-free will be censored at the latest disease assessment. The Kaplan–Meier curves will be used to summarize OS and to estimate the medians.

PFS is defined as the time between treatment initiation and first occurrence of disease progression or death, and will be censored at last follow-up if the patient remained alive without disease progression. PFS is defined as the time from the first dose of study treatment to the earlier of disease progression or death due to any cause. Patients who initiate alternate anticancer therapy in the absence of documented progression will be censored at the latest disease assessment prior to initiation of such therapy. Patients with no post-baseline disease assessments will be censored at the Cycle 1 Dose 1 date unless death occurred prior to the first planned assessment (in which case the death will be considered a PFS event). The Kaplan–Meier curves will be used to summarize PFS and to estimate the medians.

Overall response rate (ORR) is defined as the proportion of patients who achieve best overall response of complete or partial response at any time after initiation of study treatment (prior to initiation of alternate anticancer treatment). Duration of response is defined as the number of months from the time criteria are first met for either CR or PR, until the first date that PD is objectively documented. The duration of objective response will be summarized descriptively using the Kaplan-Meier method.

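### Section 7.3.4 counts surgical-cohort patients for safety only if they reach re-resection, against the all-treated safety rules elsewhere and in a cohort whose primary objective includes safety of the dose given before surgery

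*Combined protocol and SAP*

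**What the plan says.** Section 7.3.4 sets one population for both safety and efficacy in the surgical cohort: subjects dosed at least once "and undergo a craniotomy and tumor re-resection will be included in the safety and efficacy analysis for the Surgical Study Cohort Analysis".

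Four other places define the safety set by treatment, with no surgery condition:

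- Section 7.3.3: "All subjects who received at least one dose of study drug will be used for the analysis of safety data in this study".
- Section 7.2.1: "All subjects who received at least one dose of study drug and/or radiation will be used for the analysis of safety data".
- Synopsis, Study Assessments, Safety: "Subjects will be evaluated for safety if they have received any study drug".
- Synopsis, Endpoints, on all who initiate therapy (those who "receive at least one dose of ipilimumab and nivolumab and/or radiotherapy) will be evaluated for safety").

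The synopsis gives the cohort's primary objective as safety, feasibility and tolerability of neoadjuvant ipilimumab and nivolumab before re-resection, together with the T-cell pathway induction rate. Sections 2.2 and 3.2 name safety, feasibility and tolerability without that qualifier.

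Section 6.1.3 puts the first doses at C1D-29. It then states: "On C1D-15, all subjects in this cohort will undergo craniotomy and tumor re-resection".

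**The concern.** Re-resection happens after the first dose, and the toxicity under study can stop it from happening. Selecting the safety population on that later event can therefore remove the very patients the objective asks about. A patient with severe toxicity after the C1D-29 dose who never has the operation is absent from the cohort's safety result under Section 7.3.4 and present under Section 7.3.3. Two analysts following the plan could report different rates for a primary objective, and the choice could be made after the data are known.

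OS and PFS have a related weakness. Section 7.2.2 states that "OS will be determined from the time of treatment initiation until the time of death due to any cause", and PFS also runs from treatment initiation. If survival to a later operation is required for entry, every analysed patient has a guaranteed death-free interval of up to about two weeks. This is not a contradiction with Section 7.3.2, whose primary analysis is tied to the main cohort's 1-year OS. It is a weakness in the cohort-specific rule itself.

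**Working it through.** **Comparing the text.** Sections 7.2.1 and 7.3.3 both refer to safety data in this study, which includes the surgical cohort. No section adds unresected patients back to the cohort's safety set, ranks 7.3.4 against 7.3.3, or provides a separate all-dosed safety set for this cohort. The lead-in set in Section 7.3.1 is built differently. Its evaluability rule has two routes: "1) they experience a DLT at any time during the DLT evaluation period; or 2) in the absence of DLT have received". The second route goes on to ask for study drug, completed RT and the safety assessments. A patient whose treatment is cut short by a DLT therefore still counts. Section 7.3.4 has no such clause.

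**Effect on the safety rate.** Take 16 dosed (the planned cohort size), k not re-resected, j of those k with the toxicity, x events among the 16 − k re-resected, and p = x/(16 − k).

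- All-dosed rate minus 7.3.4 rate = (x + j)/16 − p = (j − k·p)/16.
- Since j lies between 0 and k and p between 0 and 1, the difference lies between −k/16 and +k/16: ±6.25 points for k = 1 and ±12.5 points for k = 2.

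Two illustrations with assumed counts show that the direction is not fixed. Both take k = 2 and 4 events among 14 re-resected, so the 7.3.4 rate is 4/14 = 28.6%.

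- Both unresected patients had the toxicity: all dosed 6/16 = 37.5%, so 7.3.4 is 8.9 points lower.
- Neither had it: all dosed 4/16 = 25.0%, so 7.3.4 is 3.6 points higher.

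**Chance that the rules give different sets.** The documents give no non-resection rate, so q is an assumption. P(at least one of 16 not re-resected) = 1 − (1 − q)^16.

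| q (assumed) | Expected number excluded | P(at least one) |
|---|---|---|
| 5% | 0.8 | 56% |
| 10% | 1.6 | 81% |
| 15% | 2.4 | 93% |
| 20% | 3.2 | 97% |

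**Effect on 1-year OS from deaths before surgery only.** Assumptions: constant hazard, and the main cohort's planning values S = 35% and 60% applied to this cohort. One year is 48 weeks (Section 7.2.2). Time to surgery is w = 1 to 2 weeks: Section 6.5.2 sets a minimum of one week, and 14 days run from C1D-29 to C1D-15.

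- P(death before surgery) = 1 − S^(w/48).
- 1-year OS among those alive at surgery = S / S^(w/48).

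| S | w (weeks) | Die before surgery | Expected of 16 | 1-year OS if alive at surgery | Change (points) |
|---|---|---|---|---|---|
| 35% | 1 | 2.16% | 0.35 | 35.77% | +0.77 |
| 35% | 2 | 4.28% | 0.68 | 36.56% | +1.56 |
| 60% | 1 | 1.06% | 0.17 | 60.64% | +0.64 |
| 60% | 2 | 2.11% | 0.34 | 61.29% | +1.29 |

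Exclusions for deterioration or withdrawal could add to this, but the documents give nothing from which to size them.

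**The case against.** The strongest reply is that the texts can be read together. Section 7.3.4 says who is included, not that only they are. Section 7.3.3 already calls for all dosed subjects in the study's safety analysis, so unresected patients would still appear in study-wide summaries and only the cohort's own table would change. That reading is available, but it does not settle the matter. The objective belongs to the cohort, and the cohort's own table would still leave those patients out.

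A second reply is that the objective is wider than the pre-surgical dose. Section 3.1.2 describes dosing before surgery and its continuation afterwards with HFRT, so a set of patients who entered the whole regimen is a recognisable choice. This is fair as far as it goes. The wider objective still covers the first dose, however, and the synopsis names that dose specifically.

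Several limits stand:

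- AE collection, DSMC review and the Section 3.5.1 boundaries (written for the 24 main-cohort patients) do not depend on 7.3.4, so patient protection is unaffected.
- The lead-in comparison concerns DLT evaluability for a continuation decision, not a general safety population. Section 6.1.1 also words that evaluability more strictly.
- The safety shift has no known direction. It is also small beside the sampling error: the exact 95% interval for 6/16 is 15.2% to 64.6%.
- The OS effect that can be calculated is small.

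**Conclusion.** The concern holds. Section 7.3.4 makes a post-dose event a condition for entering the surgical cohort's safety analysis, this conflicts with four all-treated statements, and no precedence is given. The problem is two permissible denominators for a primary objective, one of which can drop patients because of the toxicity being studied. The consequence is at most 6.25 points per missed operation among 16 dosed, of unknown sign, and nil if all are operated on. For 1-year OS the calculable part is +0.6 to +1.6 points, resting on a constant hazard and borrowed planning values. The matter concerns analysis and reporting, and it should be fixed before the data are analysed.

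**What to change.** Rewrite Section 7.3.4 so that:

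1. Safety, tolerability, OS and PFS in the surgical cohort use all subjects who receive at least one dose of study drug, in line with Sections 7.2.1 and 7.3.3 and the synopsis.
2. Only the T-cell pathway induction analysis is restricted, to subjects with the evaluable tissue it needs (inclusion criterion 7 asks for pre- and post-operative tissue).
3. The number dosed but not re-resected, or not evaluable for tissue, is reported with reasons.

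The cost is one or two paragraphs of wording and no new data, since AEs and survival are already collected for every dosed subject. The drawback is that safety, OS and PFS will have a different denominator from T-cell pathway induction. OS may look slightly less favourable, and the toxicity rate may move either way.
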